1.3.5.3 Methods of data collection

1.3.5.3.1 Base-line assessment (W⁰)

Prior to any assessments being conducted, each participant will speak on the telephone with a member of the research team and be invited to discuss any aspect of participation in the study they wish. Once informed consent has been obtained the baseline assessment will be conducted. This assessment will include a short telephone structured interview and a short self completion questionnaire. Current bowel function (based on Rome criteria), fluid and fibre intake and patients' self-perceptions of whether they are currently constipated and levels of anxiety and depression²⁸ will be elicited and data on activities of daily living²⁹, condition-specific quality of life and laxative use (both prescribed and over the counter) will be collected. A weekly structured self-completed diary will be distributed and explained. The person conducting the baseline assessment will notify practices that patients are ready to begin the intervention (as per protocol) and practices will make an appointment to see participants to start the intervention. In following this approach we minimise the risk of patients who have not given informed consent receiving the intervention as the intervention will only be delivered once a signed copy of the consent form is sent to the practice with the instruction to begin the intervention. At this first appointment, treatment per intervention protocol (1.3.5.4) will be initiated. Should patients decide to withdraw when they return to collect either their laxative prescription or for their diet and lifestyle appointment, the practice will notify the research team and all baseline assessment data and patient identification data will be destroyed or deleted from the study database.

1.3.5.3.2 Health diary (daily for 6 months from W⁰)

To minimise recall bias, data on bowel function (based on the Rome criteria)²², fluid and fibre intake, perceptions of whether constipated and use of laxatives will be gathered by a structured (tick box format) health diary, completed each day and returned monthly for six months.

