1.3.4.1 Inclusion criteria

The complexity of the revised Rome criteria for functional constipation²² militates against their use in screening for chronic constipation. Moreover, newly incident cases of constipation, especially amongst older adults, should be investigated to determine the underlying cause of the constipation and to eliminate more serious problems²³ before laxatives are prescribed.

This trial will therefore identify and recruit only 'prevalent' cases, defined in terms of those prescribed laxatives three or more times in the previous 12 months. Participants meeting this criterion will be identified from general practice computerised patient records using an electronic 'query' to interrogate repeat prescribing databases. It is recognised that the relapsing and remitting nature of constipation means that not all patients thus identified will be constipated (by objective or subjective criteria) at any given time. Eligible participants who have given informed consent will be invited to complete a baseline assessment during which current bowel function and perceptions of whether constipated will be elicited; these baseline data will be included as co-variables in our analysis (1.3.7).

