1.3.5.4 Participants' pathways through trial

		Activity
1		Potential participants identified from computerised practice databases using simple electronic query to flag individuals receiving prescriptions for constipation (3 or more in previous 12 months).
2		Initial screen by practice to identify clear exclusions.
3		Written invitation sent by practice (facilitated by research team) to patient to participate in study. Contact details form and pre-paid envelope included for patients wishing to join the study included. Research team to contact patient to answer questions and explain about process for informed consent. Consent form posted to patient with pre-paid envelope. Self completion questionnaire and pre-paid envelope also sent. Control patients will receive their diary (including pre-paid envelope) at this point.
4	W^0	When consent form is returned the telephone baseline interview will be conducted. patient advised to expect contact from practice to arrange 'intervention start' appointment.
5	W^1	Appointment at practice – laxative prescription issued or diet and lifestyle intervention initiated. All patient information and baseline data destroyed by research team if patient notifies practice of their wish to withdraw from study.
6	W^2	One week reinforcement phone call from nurse to patients randomised to personalised diet and lifestyle advice
7	W^{3-4}	Intervention fidelity measure – a small sample of patients in the standardised and personalised intervention arms of the trial will receive a short postal questionnaire to ask about the diet and lifestyle advice.
8	W^5	One month reinforcement phone call from nurse to patients randomised to personalised diet and lifestyle advice
9	W^{12}	Three month follow up outcome assessment (postal questionnaire) and collection of cost data and personal levels of success (telephone interview)
10	W^{26}	Six month follow up outcome assessment (postal questionnaire) and collection of cost data and personal levels of success (telephone interview)
11	W^{52}	Twelve month follow up outcome assessment (postal questionnaire & 1-week symptom diary). Review of practice notes to abstract data on consultation rates and prescription patterns.

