1.3.7 Statistical analysis

Analysis will be on an intention-to-treat basis. No sub-group analyses are planned. The data will be analysed using mixed effects models, accepted practice for the analysis of data from cluster randomised trials³¹. Variation between practices and variation between patients nested within practices will be fitted as random effects. The difference between treatment strategies (i.e. the three arms of the trial will be fitted as fixed effects. Most of the outcome variables (e.g. quality of life scores, number of days with (or without) symptoms are continuous and will be analysed assuming a Normal error structure. The dependent variable in each model will be point of follow-up (three, six and twelve months outcomes for quality of life, symptoms and perceptions of bowel function; twelve months for consultation and prescription rates). For each patient, baseline data will be included as a co-variate. The mixed models will be used to generate interval estimates for the differences between alternative treatment strategies.

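### The daily diary starts at W0 but treatment at W1 or later, and the days between are not designated as the baseline that discomfort-free days and adverse symptoms lack

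*Protocol*

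**What the plan says.** **Diary timing.** The protocol's diary section is titled "1.3.5.3.2 Health diary (daily for 6 months from W⁰".

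**Start of treatment.** Under 1.3.5.3.1, once the baseline assessment is done, "practices will make an appointment to see participants to start the intervention", and "At this first appointment, treatment per intervention protocol (1.3.5.4) will be initiated". The pathway table in 1.3.5.4 puts this at W1: "Appointment at practice – laxative prescription issued or diet and lifestyle intervention initiated". No upper limit on the wait is given.

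**Who is recruited.** Only prevalent cases, "defined in terms of those prescribed laxatives three or more times in the previous 12 months" (1.3.4.1), so every participant brings a history of laxative treatment.

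**What the diary feeds.** Table 1 takes bowel movements, Rome symptoms, adverse symptoms (five are named, from abdominal pain to diarrhoea) and laxative use from the diary. Section 1.3.8.2 derives discomfort-free days from diary days graded by severity of impact.

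**What baseline covers.** Section 1.3.5.3.1 lists bowel function by the Rome criteria, fluid and fibre, self-perceived constipation, anxiety and depression, and then: "data on activities of daily living²⁹, condition-specific quality of life and laxative use (both prescribed and over the counter) will be collected". No discomfort grade is listed, and the Table 1 adverse symptoms are not named.

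**Analysis.** Section 1.3.7: "For each patient, baseline data will be included as a co-variate".

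**Diary hand-out.** Section 1.3.5.3.1 distributes the diary at the baseline assessment. The pathway table sends it with the consent mailing, before W0, to patients it calls control patients, and shows no hand-out step for anyone else. The term control is not defined in this trial of three active arms.

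**The concern.** The diary clock and the treatment clock start at different times, and the protocol does not say what the days between them are for. If they are simply part of the six months, they dilute every diary contrast, and more so where practices book late.

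Those same days are also the only like-for-like pre-treatment record of two outcomes that otherwise have no named entry value. Prior laxative users may arrive with bloating or abdominal pain. Without an entry value, such symptoms cannot be separated within an arm from effects of the allocated strategy, and between-arm comparisons lose the precision that 1.3.7 plans to gain by adjustment.

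The hand-out inconsistency adds a different risk. If one arm starts its diary earlier relative to treatment than another, the share of pre-treatment days differs by arm. That shifts the contrast, whereas a common lag only shrinks it.

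**Working it through.** **1. The plan's own figure, as a check on the inputs.** From 1.3.6.3: effect 0.3 SD, power 90%, significance level 5% (two-sided assumed), ICC 0.04 (the value in the calculation sentence), 25 patients per practice.

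- Per arm without clustering: 2 × (1.960 + 1.282)² / 0.3² = 233.5, so 234.
- Design effect: 1 + (25 − 1) × 0.04 = 1.96.
- Practices per arm: 234 × 1.96 / 25 = 18.35, so 19, or 57 in total. This reproduces.
- Effective patients per arm at 19 × 25: 475 / 1.96 = 242.3. Power = Φ(0.3 × √(242.3/2) − 1.96) = 91.0%.

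**2. Share of the diary before treatment.** Six months is taken as 182 days and three months as 91. At the scheduled W1 start the share is 7/182 = 3.8% of the whole diary, and 7/91 = 7.7% of the part up to three months.

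**3. Dilution if those days are counted.** With no between-arm difference before treatment, the observed effect is d × (1 − lag/182). The documents give no effect size for diary outcomes, so the 0.3 SD and ICC 0.04 of the primary outcome are borrowed as an illustration. Lags beyond 7 days are assumptions.

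| Lag | Share of 182 days | Observed effect | Power |
|---|---|---|---|
| 0 days | 0% | 0.300 SD | 91.0% |
| 7 days (scheduled) | 3.8% | 0.288 SD | 88.8% |
| 14 days | 7.7% | 0.277 SD | 86.2% |
| 28 days | 15.4% | 0.254 SD | 79.8% |

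At the scheduled lag the loss is 91.0 − 88.8 = about 2 percentage points.

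**4. If the share differs by arm.** Suppose two arms produce the same change from earlier management, 0.3 SD per diary day (assumed). The spurious difference is 0.3 × (difference in share). If one arm starts its diary a week before treatment and the other on the day of treatment, this is 0.3 × 7/182 = 0.012 SD. If waits are 7 and 21 days, it is 0.3 × 14/182 = 0.023 SD. Both are small, but neither shrinks with more patients.

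**5. What a diary baseline might gain.** If the pre-treatment mean correlates r with the later diary mean, adjustment removes r² of patient-level residual variance: 9% at r = 0.3 and 36% at r = 0.6. These correlations are assumed. The gain is smaller where the existing baseline items already explain part of the variance.

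**6. Which outcomes lack a baseline.** Setting Table 1 and 1.3.8.2 beside 1.3.5.3.1: bowel function, fluid and fibre, perceived constipation, laxative use and condition-specific quality of life all have entry values. The discomfort grade does not, and the adverse symptoms are not named.

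**The case against.** Much of the case on the other side stands.

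- **The early days are themselves a pre-treatment value.** A reader might infer that discomfort and adverse symptoms have none at all. The documents do not support that: a diary running from W0 records them before treatment. What is missing is their designation as baseline.
- **No section says the early days are counted as outcome.** Section 1.3.5.3.2 fixes when the diary is completed, and 1.3.7 speaks of outcomes at points of follow-up. Counting from W0 is the natural reading of a six-month diary, but the counting window could be set in a statistical analysis plan that is not shown. The baseline content and the diary hand-out, by contrast, are fixed in the protocol itself.
- **Recruitment is a legitimate origin under intention to treat.** Sections 1.3.5.1 and 1.3.5.2 time the other outcomes from recruitment, and a short wait is part of a pragmatic strategy. This argues against moving the six-month clock to the appointment. That date may depend on the arm, since the personalised visit takes 30 to 45 minutes and the standardised one at most 10, and moving the clock would take the diary off the questionnaire and cost schedule.
- **Carried-over symptoms do not by themselves bias the comparison.** All arms recruit by the same prescribing criterion, so under randomisation such symptoms are expected equally. Omitting the adjustment costs precision.
- **The gap in adverse symptoms may be partial.** The preferred quality-of-life instrument may cover some abdominal symptoms. The documents do not show its items.
- **A diary baseline would be taken unblinded, after practice randomisation.** Patients may change behaviour before the appointment, and adjustment could then remove a little of the effect. This is a real cost, though the baseline measures the plan already adjusts for are also collected after practice randomisation.

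**Conclusion.** The point holds as a modest design improvement. The diary starts at W0, treatment starts at W1 or later, and discomfort-free days and adverse symptoms have no designated baseline covariate although 1.3.7 promises one for each patient. On the natural reading, 3.8% of the six-month diary reflects earlier management at the scheduled lag. That costs about 2 points of power under the borrowed 0.3 SD and ICC 0.04; larger losses need longer waits, which the documents neither state nor exclude.

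Sections 1.3.5.3.1, 1.3.5.3.2 and 1.3.5.4 do not agree on when each arm receives the diary. They show that the pre-treatment share may differ by arm, not that it does.

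A reader might go further and infer that the trial's main result is at risk. It is not: the primary outcome is a questionnaire score with its own baseline value, and neither it nor the sample size uses the diary.

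**What to change.** 1. Reconcile 1.3.5.3.1, 1.3.5.3.2 and 1.3.5.4 so that the diary starts at W0 in all three arms, and replace or define the term control. This comes first, because the next steps need pre-treatment days in every arm.
2. Record the booked date of the first appointment for every participant, whether or not it is kept, and fix in advance what is done if no date is booked.
3. Use the per-day diary values before that date as the baseline covariate for the matching diary outcomes, chiefly discomfort-free days and adverse symptoms. Leave those days out of the outcome rate, expressed per diary day. The diary must carry the adverse-symptom and discomfort items from its first day; the content list in 1.3.5.3.2 does not name them, although Table 1 and 1.3.8.2 rely on them.
4. Keep the W0 to W26 schedule, so that diary outcomes stay aligned with the questionnaires and cost data, and report the count from recruitment as a sensitivity analysis.

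**Cost.** No new instrument and no extra contact: one recorded date and a stated rule. The outcome period loses the days before the appointment (182 − 7 = 175 days remain at the scheduled lag). The baseline is short and noisy and is taken unblinded after practice randomisation, and the gain in precision depends on a correlation that the documents do not give.

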1.3.5.3.3 Follow-up self-completion questionnaires (W¹³ and W²⁶ and W⁵²)

Follow-up questionnaires, using up to two reminders, will be sent at W¹¹ (for completion by W¹³), W²⁴ (for completion by W²⁶) and W⁵⁰ (for completion by W⁵²). Data to be collected will be: condition-specific quality of life (1.3.5.1); Rome criteria²²; and anxiety and depression²⁸.

Although structured interviews are the gold standard for collecting a large volume of complex data³⁰, the choice of postal questionnaires has been made to contain the cost of data collection. The use of postal questionnaires will also allow some blinding of outcome assessment (1.3.5.5).

Our recent experience in using postal questionnaires to gather information on quality of life and costs of treatment from ambulant, cognitively normal, older people with angina, in which we achieved response rates of 72%, 83% and 90% at baseline, 12-month and 24-month follow-up respectively, suggests that non-response bias will not be a significant problem.

1.3.5.3.4 Telephone interviews (W^{3-4} , W^{13} and W^{26})

Within two weeks of their consultation for diet and lifestyle advice a small sample of patients in the standardised and personalised intervention arms of the trial will receive a short postal questionnaire to ask about the diet and lifestyle advice they were given. The purpose being to monitor the content of the interventions. Short telephone interviews will be used to collect cost data on medication purchase (both prescribed and OTC), and other out of pocket expenses for the economic analysis. This interview will also ask patients about their personal levels of success in the management of their constipation. They will be conducted by a research secretary at W^{13} and W^{26} and data will be recorded directly onto a database by the interviewer. We are currently using this method effectively in a study of older people. Other resource use data will be collected from practice medical records (1.3.5.3.5).

1.3.5.3.5 Medical records (W^{52})

Data pertaining to consultation rates and prescription of laxatives for all study participants for the twelve months post recruitment will be abstracted from medical records. This will be done practice-by-practice at the end of the data collection period. Trained research nurses will interrogate paper-based and computerised records and will enter data directly to a database on lap-top computer. The electronic query used to identify patients at the beginning of the trial will be adapted to capture data on laxative prescriptions. We have used these methods of data collection to good effect in previous similar studies.

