1.3.4.2 Exclusion criteria

- Patients resident in long-term care.
- Patients with inflammatory bowel disease, intestinal obstruction/bowel strictures, known colonic carcinoma, and conditions contra-indicative to the prescription of laxative preparations²⁴.
- Inability to read and understand written treatment plans and educational material.
- Inability to complete outcome assessments, even with assistance (e.g. major cognitive impairment, lack of understanding of English).

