1.3.5 Assessment of outcomes

1.3.5.1 Outcome measures

The primary outcome, and the criterion upon which the sample size calculations have been based, is patient-reported condition-specific quality of life at three months post recruitment (1.3.5.2). Our preferred measure of quality of life is the constipation-specific PAC-SYM / PAC-QOL²⁵, which has been demonstrated to have good validity and reliability. However, this measure is not utility-based. For the purposes of the economic evaluation (1.3.8), a measure of the utility placed by patients on

their health state will be required. The condition-specific measure of quality of life will therefore be supplemented by the generic, utility-based EQ-5D^{26;27}.

Secondary outcomes will include: bowel movement frequency; the presence/absence of the other Rome criteria for constipation; patients' own perceptions of whether or not they are constipated; patient satisfaction with bowel function; adverse effects of treatment; relapse / re-consultation rates; fluid and fibre intake (Table 1).

In addition, the cost implications of the condition and its treatment (e.g. GP consultations, purchase of prescribed and over-the-counter medication) will be assessed, as part of the economic evaluation (Table 2; section 1.3.8).

Table 1 Outcome measures

Primary outcome	Measurement method	When	Where
Health-related quality of life	Postal questionnaire	At three months post recruitment	Participant's home
Secondary outcomes	Measurement method	When	Where
Health-related quality of life	Postal questionnaire	At six and twelve months post recruitment	Participant's home
Number of bowel movements per week	Self-completed structured diary + Postal questionnaire	Daily for 6 months At 12 months	Participant's home
Other Rome criteria: straining at defecation, stool consistency, perceived incomplete evacuation	Self-completed structured diary + Postal questionnaire	Daily for 6 months & for 1 week at 12 months At 12 months	Participant's home
Subjective perception of whether constipated; satisfaction with bowel function	Telephone interview + Postal questionnaire	At 3 months At 6 months & 12 months	Participant's home
Adverse events: abdominal pain, nausea, bloating, flatulence, diarrhoea	Self-completed structured diary + Postal questionnaire	Daily for 6 months & for 1 week at 12 months At 12 months	Participant's home

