1.3.9 Ethical arrangements

Approval for this study will be sought from Scotland A Multicentre Research Ethics Committee (MREC) and subsequently from the relevant Local Research Ethics Committees. We will follow the recommendations of the MREC (the Medical Research Council and Consumers for Ethics in Research (CERES) in conducting this trial and in providing participants with appropriate information.

The risks to patients are anticipated to be minimal (particularly since the option of rescue medication is available to those allocated to the diet and lifestyle arms). Conversely, there are potential benefits in terms of symptom relief and enhanced quality of life for all participants (since all groups get an 'active' intervention and are not denied treatment). Written information leaflets will be used to inform those invited to participate about the potential benefits, risks and implications of participation, and this written information will be reinforced by the nurse when patients are invited to participate. Those invited to participate will have a minimum of a week to consider whether they wish to join the study. Affirmation of consent (for participation in the trial and for access to medical records) will be requested at the follow-up consultation (1.3.5.4) and baseline data from those withholding consent will be destroyed. We do not anticipate that anyone eligible for the study would be incapable of giving fully informed consent. The University of Newcastle recommends that original research data be retained for a minimum of ten years and we will follow this recommendation. All data will be held in compliance with the requirements of the Data Protection Act.

Hutton³⁵ has suggested that cluster randomised trials pose unique ethical issues. In particular, since randomisation in this trial is at the level of the practice, patient consent must essentially be post-randomisation. As stated above, we believe that the offer of rescue medication to patients in practices allocated to the diet and lifestyle arms will go some way to ameliorating this constraint on patient choice.

2 Reference List

Reference List

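### Adverse events rest on patient-reported symptoms, and the week-52 records review has no field for death or hospital admission, so neither could be reported by arm or costed

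*Protocol*

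**What the plan says.** Section 1.3.5.1 lists among the secondary outcomes "adverse effects of treatment; relapse / re-consultation rates; fluid and fibre intake". Table 1 spells out the first of these as "Adverse events: abdominal pain, nausea, bloating, flatulence, diarrhoea". The sources are the self-completed diary (daily for six months, then one week at 12 months) and the postal questionnaire at 12 months.

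The week-52 records review is described in section 1.3.5.3.5: "Data pertaining to consultation rates and prescription of laxatives for all study participants for the twelve months post recruitment will be abstracted". Table 1, Table 2, section 1.3.5.2, the pathway table in 1.3.5.4 and section 1.3.8.3 describe it in the same terms: consultations, and prescriptions of laxatives (in 1.3.8.3, drugs prescribed). Trained research nurses carry it out on paper and computerised records. Section 1.3.9 already seeks consent for access to those records.

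Section 1.3.8.3 says that NHS costs are to cover delivery of the three strategies and participants' later use of services. The items it names are laxatives, GP and nurse consultations, and the delivery of and training for the advice packages.

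**The concern.** The three strategies are to be compared on clinical effectiveness and cost over 12 months. A reader of the results would expect to learn how many participants in each arm died or were admitted to hospital, and whether any admission was for a bowel complication. The planned data cannot answer that.

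Symptom reports depend on patients completing and returning forms, and a patient who dies or becomes seriously ill is likely to stop. In the patient-returned data, such a participant looks the same as one who simply stopped replying. The records review would not have this weakness, but it has no field for these events.

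The economic analysis is affected too. Section 1.3.8.4 recommends the cheaper strategy when utilities or discomfort-free days do not differ, and otherwise computes cost-effectiveness ratios. An admission costs the NHS money, and leaving admissions out could tilt either result if they differ between arms.

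A statistical analysis plan could not repair this, because it cannot analyse fields that were never abstracted.

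**Working it through.** **Denominators.** The claim rests on no figure stated in the plan, but the number of practices sets the size of the records review, so I checked it first. Inputs from section 1.3.6.3 are effect size 0.3 SD, 90% power, 5% significance (taken as two-sided), ICC 0.04 and 25 patients per practice.
- Individually randomised: 234 per arm.
- Design effect: 1 + (25 − 1) × 0.04 = 1.96.
- 234 × 1.96 = 458.64; 458.64 / 25 = 18.3, so 19 practices per arm and 57 in total. The stated figure reproduces.
- Recruits: 57 × 30 = 1,710, or 19 × 30 = 570 per arm.
- Expected with 12-month data: 57 × 25 = 1,425.
- Expected without: 1,710 − 1,425 = 285, which is 5 in 30 (16.7%).

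**What each source would show about harm.**

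| Source | Planned content | Needs the patient to respond? | Death or admission identifiable? |
|---|---|---|---|
| Diary (Table 1, 1.3.5.3.2) | five symptoms | yes | no |
| Discomfort-free days (1.3.8.2) | graded impact of symptoms and side-effects, from the diary | yes | no |
| Questionnaire (Table 1, 1.3.5.3.3) | five symptoms at 12 months | yes | no |
| Telephone interview (1.3.5.3.4) | costs to the patient, personal success | yes | no |
| Records review (1.3.5.3.5) | consultations, laxative prescriptions | no | no |

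Two details bear on this table.
- Section 1.3.5.3.4 opens its account of the interviews with "Short telephone interviews will be used to collect cost data on medication purchase (both prescribed and OTC), and other out of pocket expenses" and sends other resource use to section 1.3.5.3.5, which lists only consultations and laxative prescriptions. The cross-reference adds no field for admissions.
- The content lists do not match Table 1. The items that section 1.3.5.3.2 says "will be gathered by a structured (tick box format) health diary, completed each day and returned monthly for six months" are bowel function, fluid and fibre, perceived constipation and laxative use. Section 1.3.5.3.3 says "Data to be collected will be: condition-specific quality of life (1.3.5.1); Rome criteria²²; and anxiety and depression²⁸". Neither list names adverse events. I have taken Table 1 as governing, which is the reading more favourable to the plan.

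**Time covered.** Daily recording runs for 26 weeks (182 days) plus one week (7 days): 189 / 365 = 51.8%. The remaining 176 / 365 = 48.2% has no contemporaneous symptom recording. For that stretch the sources are the 12-month questionnaire, looking back, and the records review.

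**What the added fields could and could not deliver.** Assume complete ascertainment and ignore clustering.
- Zero events in one arm of 570 gives a one-sided 95% upper bound of 1 − 0.05^(1/570) = 0.52%. Zero in all 1,710 gives 1 − 0.05^(1/1710) = 0.18%.
- For a comparison of two arms, take 2% against 5% as an illustration. The standard error is √[(0.02 × 0.98 + 0.05 × 0.95) / 570] = √(0.0671 / 570) = 0.01085. Then 0.03 / 0.01085 = 2.76 and 2.76 − 1.96 = 0.80, so power is about 79%. Clustering would lower it.

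So only a large difference would be detectable. The fields would support a descriptive table and an upper bound, not a test.

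**The case against.** The strongest reply is that this is a low-risk pragmatic trial and the plan contradicts nothing. Patients in the diet and lifestyle arms may continue laxatives if they need them (1.3.3.1, repeated as rescue medication in 1.3.6.4 and 1.3.9), with use recorded in the diary. Section 1.3.5.2 defends the follow-up schedule as a balance between patient burden and longer-term assessment. A serious event that leads to a GP visit would add to the consultation count. The trial could not compare rare events in any case.

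All of that is fair, and it rules out several stronger readings.
- **That the trial should test its risk statement.** Section 1.3.9 says "The risks to patients are anticipated to be minimal". That is an expectation offered in an ethics section, partly because rescue medication is available; it is not a hypothesis.
- **That the protocol itself flags serious bowel disease as a likely treatment effect.** It does not. The mention of serious underlying causes in 1.3.4.1 concerns newly incident cases, which are not recruited. The exclusions in 1.3.4.2, such as "intestinal obstruction/bowel strictures, known colonic carcinoma", are entry criteria. Nothing supports treating new carcinoma or inflammatory bowel disease as an outcome of the interventions.
- **That a particular number of serious events would be missed.** The protocol gives no rate, and any count would be invention.
- **That serious events would be wholly invisible, or would lower every count.** They might raise the consultation count, though without a reason attached. Loss through non-return affects only patient-reported data.
- **That nurses read the whole record anyway, so the addition is free.** Section 1.3.5.3.5 does not say so, and laxative prescriptions are to be captured by an adapted electronic query.

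What the reply does not remove is the missing field. Permission to continue laxatives lowers the concern about harm; it does not record whether harm occurred. The burden argument concerns patients, and a records field places none on them.

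**Conclusion.** The point stands as a gap in data collection that is cheap to close. As written, the trial would report five patient-reported symptoms and could not state deaths, hospital admissions or serious bowel events by arm. Admission costs would be left out of an NHS cost total whose stated scope includes later service use. The gap covers all 1,710 planned recruits over 12 months, and matters most for the 285 or so expected to stop providing data.

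This rests on two readings: that the records review abstracts what the protocol consistently says it abstracts and no more, and that Table 1 governs the content of the diary and questionnaire. It assumes no event rate and does not claim that any arm is unsafe.

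**What to change.** Before abstraction starts, add two items to the week-52 form in section 1.3.5.3.5:
- death, with date;
- hospital admission, with date and reason, so that obstruction or faecal impaction can be identified.

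Collect them identically in all three arms, for every participant who has not refused access to records, including those who stopped returning diaries or questionnaires. Those who withdraw at the first appointment, whose data are to be destroyed under 1.3.5.3.1, fall outside this. Tabulate both items by arm as descriptive safety data, with no formal test, and add admissions to the NHS costs in 1.3.8.3. Carry the same wording into Tables 1 and 2 and the pathway table. In the same edit, bring the content lists in 1.3.5.3.2 and 1.3.5.3.3 into line with Table 1 on adverse events.

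The cost is some extra time per record, since an admission reason may need manual reading. The protocol gives no basis for putting a figure on it. No visit, treatment, sample size or patient-completed form changes, apart from any adverse-event items that Table 1 already requires.
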